10.1 Disposition of Subjects and Discontinuations

All tables and listings related to disposition of subjects and discontinuations will be generated using SCR analysis set.

A primary table of Subject Disposition will provide the overall summary of the analysis sets by dose level and overall:

- Number of screened subjects*
- Number of subjects discontinued prior treatment start (overall and by reason)*
- Number of subjects who continued beyond screening
- Number of subjects who completed treatment with M3541 ("M3541 Termination" eCRF page)
- Number of subjects who completed treatment with RT ("Radiotherapy Termination" eCRF page)
- Number of subjects discontinued from M3541 overall and by reason ("M3541 Termination" eCRF page)
- Number of subjects discontinued from RT overall and by reason ("Radiotherapy Termination" eCRF page)
- Number of subjects who completed the trial ("Study Termination" eCRF page).
- Number of subjects discontinued from trial overall and by reason ("Study Termination" eCRF page).

A second summary table on analysis sets will be generated:

- Number of subjects in Screened Analysis Set*
- Number of subjects in DLT Analysis Set (Overall and per dose level)

- Number of subjects in SAF Analysis Set (Overall and per dose level)
- Number of subjects in PKS Analysis Set (Overall and per dose level)
- Number of subjects in BMK Analysis Set (Overall and per dose level)

A third summary table will display the number of subjects overall, in each country and in each site (per analysis set).

A listing of subject disposition will include the following information (as applicable): dose level, subject identification number (ID), date and version of ICF, protocol version, reason for screen failure, date of first and last dose of M3541 and RT, SAF analysis set, DLT analysis set, BMK analysis set and PKS analysis set.

A second listing will include the following trial discontinuation information: dose level, subject ID, end of trial status (completed, ongoing, discontinued), the reason for trial discontinuation, the last follow-up date on trial, and the date of first and last dose of M3541 and RT.

A third listing will include the following M3541 and RT discontinuation information: dose level, subject ID, end of treatment status (completed, ongoing, discontinued), the reason for M3541 and/or RT discontinuation, and the date of first and last dose of M3541 and RT.

10.2 Protocol Deviations

10.2.1 Important Protocol Deviations

Listings of protocol deviations will be generated on the safety population by displaying following information:

- Listing of important protocol deviations: dose level, subject ID, deviation type and description as displayed in CTMS.
- Listing of deviations from treatment compliance (subjects with less than 80% of compliance): dose level, subject ID, compliance with M3541 (%), compliance with RT (%), first and last dose date for both M3541 and radiotherapy. Compliance will be derived using the algorithm reported in section 13.

10.2.2 Reasons Leading to the Exclusion from an Analysis Set

For subjects and data excluded from DLT, PKS, and BMK analysis sets, the reasons for exclusion will be listed.

^{*}These will be reported in the overall column only.

11 Demographics and Other Baseline Characteristics

Population: SAF Analysis Set

All demographics and baseline characteristics will be listed and summarized by dose level and overall using SAF analysis set.

11.1 Demographics

The following demographic characteristics will be summarized using the information from the "Demographics" eCRF page.

- Sex: male, female
- Race: Black of African American, Asian, American Indian or Alaska Native, Native Hawaiian or other Pacific Islander, White, Other, Not collected at this site
- Ethnicity: Hispanic or Latino, Not Hispanic or Latino
- Age (years): summary statistics

Specifications for computation:

- Age [years]:
 - o (date of given informed consent date of birth + 1) / 365.25
 - In case of missing day for at least one date, but month and year available for both dates:
 - For the derivation of age, the day of informed consent and the day of birth will be set to 1 and the formula above will be used
 - o In case of missing month for at least one date, but year available for both dates: For the derivation of age, the day and the month of informed consent and the day and month of birth will be set to 1 and the formula above will be used

A listing of demographic data will include the following information: dose level, subject ID, sex, race, ethnicity, date of birth and age in years.

11.2 Medical History

Population: SAF analysis set

The medical history will be summarized from the "Medical History" eCRF page, using the most recent available version of MedDRA (version 20.0 or later) preferred term (PT) as event category and MedDRA system organ class (SOC) body term as body system category.

Medical history will be displayed in terms of frequency tables: ordered by primary SOC and PT in alphabetic order.

A supportive listing of Medical History data by subject will include all the relevant data fields as collected on the "Medical History" eCRF page.

11.3 Other Baseline Characteristics

Population: SAF analysis set

The following baseline characteristics will be summarized using the information from the "Vital Signs" and "ECOG performance status" eCRF pages:

- Height (cm)
- Weight (kg)
- ECOG Performance status

A listing of baseline characteristics will include the following information: dose level, subject ID, height in cm, weight in kg, ECOG performance status, results for HIV, Hepatitis B and Hepatitis C virus test with methods used (from "Serology" eCRF page).

Additionally a listing of disease history will be provided including all relevant data from the "Disease History" eCRF page.

12 Previous or Concomitant Medications/Procedures

Population: SAF Analysis Set

12.1 Prior Anti-Cancer Treatments and procedures

The prior anti-cancer treatments and procedures are collected under the "Prior anti-cancer drug therapies", "Prior anti-cancer surgeries", and "Prior anti-cancer radiotherapy" eCRF pages.

The following listings of prior anti-cancer treatments and procedures will be provided:

- Listing of prior anti-cancer drug therapies;
- Listing of prior surgeries;
- Listing of prior radiotherapy.

These will include the subject ID, dose level and all the relevant collected data fields on the corresponding eCRF pages.

12.2 Previous Medications

Previous medications are medications, other than trial medications, which started before first administration of trial treatment.

Previous medications will be summarized from the "Concomitant medications" eCRF page. The Anatomical Therapeutic Chemical (ATC)-2nd level and PT will be tabulated as given from the

World Health Organization Drug Dictionary (most recent available version of WHO-DD, Sept. 2016 or later). In case multiple ATC's are assigned to a drug, all ATC-2nd level will be used for reporting.

In case the date values will not allow to unequivocally allocate a medication to previous medication, the approach described at section 9 will be followed.

Previous medications will also be listed. The listing will include: subject ID, dose level and all corresponding collected data fields on the corresponding eCRF page.

12.3 Concomitant Medications

Concomitant treatments are medications, other than trial medications, which are taken by subjects any time on-trial (on or after the first day of M3541 treatment for each subject) or within 30 days after last dose of M3541 treatment (PTD 30). Medications started after 30 days will be presented and flagged in listings but will not be taken into account in summary tables. Medications started on treatment day 1 will only be considered concomitant.

Concomitant medications will be summarized from the "Concomitant medications" eCRF page. The ATC-2nd level and PT will be tabulated as given from the most recent available version of WHO-DD, Sept. 2016 or later. In case multiple ATC's are assigned to a drug, all ATC-2nd level will be used for reporting.

In case the date values will not allow to unequivocally allocate a medication to concomitant medication, the approach described at section 9 will be followed.

Concomitant medications will also be listed. The listing will include: dose level, subject ID and all corresponding collected data fields on the corresponding eCRF page.

12.4 Concomitant Procedures

Concomitant procedures are procedures which are undertaken any time on-trial. These will be listed according to the CRF page "Concomitant Procedures".

In case the date values will not allow to unequivocally allocate a procedure to concomitant procedure, the approach described at section 9 will be followed.

The listing will include: dose level, subject ID and all corresponding collected data fields on the corresponding eCRF page.

12.5 Pain Therapy

Pain therapy results will be listed according to the CRF page "Pain Therapy". The listing will include: subject ID, dose level, date and fraction day, medication change and flag for new therapy given.

12.6 Anti-cancer, radiotherapy and surgery post-treatment

Anti-cancer, radiotherapy and surgery post-treatment will be listed according to "Anti-cancer treatment after discontinuation", "Radiotherapy after discontinuation" and "Surgery after discontinuation" eCRF pages. The 3 listings will include: subject ID, dose level and all corresponding collected data fields on the corresponding eCRF page.

13 Treatment Compliance and Exposure

Population: SAF Analysis Set

Treatment compliance and exposure will be listed and summarized by dose level and overall using SAF analysis set.

All dosing calculations and summaries will be based on "M3541 Administration" and "Radiotherapy Administration" eCRF pages.

Subjects should receive treatment with M3541 at a starting dose of 50 mg QD, which should be given 1 hour and 45 minutes (+/- 15 minutes) before each RT fraction (3 Gy) for up to 10 fractions. Based on nonclinical assumptions, the pre-planned dose levels are 50, 100, 200, 300, 500, and 800 mg; however, the number of dose levels and the actual dose to be explored in each subsequent cohort remains to be determined.

Number of days of therapy

The number of fraction days of Radiotherapy treatment and the number of days of M3541 therapy will be summarized by dose level.

Additionally, number and percentage of subjects in the following exposure categories will be reported by dose level:

- [1 day 4 days]
- [5 days 7 days]
- [8 days 9 days]
- 10 days
- > 10 days

Cumulative dose

The cumulative dose (mg) of M3541 will be calculated as the sum of the total daily doses that the subject received.

The cumulative dose (Gy) of RT will be calculated as the sum of the total daily doses that the subject received.

Compliance with treatment

The compliance with the treatment is defined as:

For M3541:

Relative dose intensity (%) =
$$\left(\frac{\text{cumulative dose (mg)}}{10 * \text{planned daily dose (mg)}} * 100\right)$$

• For RT:

Relative dose intensity (%) =
$$\left(\frac{\text{cumulative dose (y)}}{10 * \text{planned daily dose (y)}} * 100\right)$$

The compliance with the treatments will display using the following categories:

- > 100%
- 100%
- [80% 100%[%[
- [65% 80% [
- [50% 65% [
- < 50%

The following summary tables will be provided for M3541 and RT administrations by dose level:

- Number of fraction days for Radiotherapy and number of days of M3541 therapy
- Cumulative dose (mg for M3541 and Gy for RT) and relative dose intensity

The listing of exposure assessments for each M3541 and RT administration (including e.g. start and stop date and time of administration, dose, frequency, change in dose) will be provided by subject as recorded from the related eCRF pages.

14 Efficacy Analyses

Efficacy endpoints include Best Overall Response (BOR), Progression Free Survival (PFS), Sum of the Lesion Diameter (SoLD) for irradiated lesions, and location of disease progression.

14.1 Best Overall Response

Population: SAF Analysis Set

The tumor response assessment will be based on "Assessment of disease based on imaging (according to RECIST 1.1)" eCRF page.

The Best Overall Response (BOR) is defined as the best response across all time points evaluated per RECIST 1.1, assessed locally by the investigator every 6 weeks (starting on PTD 42) for the

first 6 months, then every 12 weeks thereafter until determination of Progressive Disease (PD), using the investigator-reported overall response per time point and excluding assessments after tumor surgery.

The order to obtain the BOR is the following: Complete Response (CR), Partial Response (PR), Stable Disease (SD), Progressive Disease (PD), and Not Evaluable (NE). For example, a subject who has SD at the first assessment, PR at the second assessment, and PD at the last assessment has a BOR of PR.

To be considered the best response, SD must also meet the minimum 6 weeks (-7 days) from first day of treatment. If the minimum time is not met, the subject's best overall response depends on the subsequent assessments. For example, a subject who has SD at the first assessment, PD at the second assessment and does not meet the minimum duration for SD, will have a best overall response of PD. The same subject lost to follow-up after the first SD assessment would be considered NE for BOR.

If a subject has missing baseline tumor assessment and/or no tumor assessment on-treatment, BOR will be NE.

The confirmed BOR (BORc) will be also analyzed. In this case, CR and PR need to be confirmed at a subsequent assessment, at least 4 weeks after initial overall response assessment of CR/PR.

Both confirmed and unconfirmed BOR will be summarized by tabulating the number and percentage of subjects with CR, PR, SD, PD or NE.

The Objective Response Rate (ORR) is defined as the proportion of subjects with BOR of PR or CR, and it will be tabulated for both confirmed and unconfirmed BOR by dose level, with 95% CI, calculated using the Clopper-Pearson method.

A spider graph will display the percentage change from baseline in tumor size, defined as sum of lesion diameters (longest for non-nodal lesions, short axis for nodal lesions) for all target lesions (as reported in the "Sum of diameters (according to RECIST 1.1)" eCRF page), against the treatment day for each subject per dose level. Subjects with no baseline tumor assessment or without any post-baseline tumor assessment will not be included.

In addition, waterfall plots with all subjects from all cohorts will be provided. Bar height will represent the best percentage change in tumor size from baseline per subject. The confirmed BOR will also be presented as an annotation on each vertical bar. Subjects with no baseline tumor assessment or without any post-baseline tumor assessment will not be included.

The listings of tumor assessments (including e.g. lesion number and site, type of lesion, imaging date and relative day, assessment method, size in mm) and tumor responses (including e.g. sum of diameter of target lesions, response for each lesion class, overall response) will be provided by subject as recorded from the "Target Lesions", "Sum of Diameters", "Non-Target Lesions", "Non-Target Lesions" and "Assessment of disease based on imaging" eCRF pages. Additionally, both will include: dose level, first/last M3541 dosing date, BOR (confirmed and unconfirmed), site of primary tumor and TNM status at study entry.

Finally, a listing reporting information on irradiated lesion location will be populated using information from "Irradiated Lesions Location" and "Radiotherapy" eCRF pages.

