- m. Tumor imaging by CT, MRI, or bone scan at baseline to document extent of lesions according to RECIST 1.1. Baseline tumor evaluation can be up to 28 days old when treatment starts. A brain CT / MRI scan (either, contrast preferred) is required at Screening if not performed within the previous 6 weeks.
- n. Tumor assessments using the same method used at baseline are to be completed every 6 weeks beginning on PTD 42 of the Mid-term Safety Follow-up period through the Long-term Safety Follow-up period (ie, PTD 180) for a total of 4 assessments. During the survival follow-up period (ie, PTD 181 to 365) tumor assessments will occur approximately on PTD 270 and PTD 365. Assessments are not required if the subject has started a new antitumor treatment. If a new treatment is started, the date (and regimen) must be reported in the eCRF.
- o. See Table 4 for details of PK blood sampling.
- p. FD 1 only; see Table 4 for details.
- q. FD 5 and 10; see Table 4 for details.
- r. CCI

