Presentation of pharmacokinetic/biomarker concentration data

Pharmacokinetic/biomarker concentration data will be descriptively summarized per dose level using: number of non-missing observations (N), arithmetic mean (Mean), SD, coefficient of variation (CV%), Min, median, and Max.

Descriptive statistics of PK/biomarker concentration data will be calculated using values with the same precision as the source data, and rounded for reporting purposes only. The following conventions will be applied when reporting descriptive statistics of PK/biomarker concentration data:

Mean, Min, Median, Max: 3 significant digits

SD: 4 significant digits

CV%: 1 decimal place

Presentation of pharmacokinetic parameter data

Pharmacokinetic parameter data will be descriptively summarized per dose level using: N, Mean, SD, CV%, Min, Median, Max, geometric mean (GeoMean), and the geometric coefficient of

variation (GeoCV) and the 95% CI for the GeoMean (lower CILCI 95% GeoMean, Upper CIGM, UCI 95% GeoMean).GM)

The following conventions will be applied when reporting descriptive statistics of PK parameter data:

Mean, Min, Median, Max, GeoMean, 95% CI: 3 significant digits

SD: 4 significant digits

CV%, GeoCV%: 1 decimal place

Definition of baseline:

The last non-missing measurement prior to first administration of M3541 will be used as the baseline measurement.

Definition of treatment day:

Treatment day 1 is defined as the date of first administration of M3541, the day before is defined as Treatment day –1 (no Treatment day 0 is defined).

Definition of fraction day:

Fraction days are defined as days of radiotherapy administration.

Definition of on-treatment period for safety analyses:

On-treatment period for safety analyses will be the time from the Treatment day 1 until the last M3541 administration date + 30 days (PTD 30), the earliest date of subsequent anticancer drug therapy minus 1 day or the clinical cut-off date (if the treatment is still ongoing), whichever occurs first.

Subsequent anticancer drug therapy date will be based on "Anti-cancer treatment after discontinuation", "Radiotherapy after discontinuation", and "Surgery after discontinuation" eCRF pages.

Definition of duration:

Duration will be calculated by the difference of start and stop date + 1 (e.g. survival time (days) = date of death – date of first dose + 1), if not otherwise specified.

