UNK	UNK	> Treatment start (year) and <= Treatment end + 30 days (year)	After treatment start	Concomitant
UNK	<= Treatment start (month and year)		Before treatment start	Previous
UNK	<= Treatment start (month and year)		After treatment start	Previous and concomitant
UNK	> Treatment start (month and year) and <= Treatment end + 30 days (month and year)		After treatment start	Concomitant
<= Treatment start (date)			Before treatment start	Previous
<= Treatment start (date)			After treatment start	Previous and concomitant
> Treatment start (date) and <= Treatment end + 30 days (date)			After treatment start	Concomitant

UNK = Unknown

Handling of unscheduled and early termination visit assessments:

As a general rule, unscheduled assessments will always be included in the analysis.

Early termination visit assessments will be analyzed according to the treatment day of collection, as defined above.

10 Trial Subjects

The subsections in this section include specifications for reporting subject disposition and treatment/trial discontinuations. Additionally, procedures for reporting protocol deviations are provided.

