14.2 Progression Free Survival Time

Population: SAF Analysis Set

Progression Free Survival (PFS) time is defined as the time (in months) from first administration of trial treatment until the first date of PD or death due to any cause.

It will be based on "Assessment of disease based on imaging (according to RECIST 1.1)", "Survival follow-up / Progression disease", "Subject Status / Survival Follow-up", "Anti-cancer treatment after discontinuation", "Radiotherapy after discontinuation", "Surgery after discontinuation" and "Death" eCRF pages.

PFS will be censored in the following scenarios:

- Subjects who do not experience an event (PD or death) will be right-censored on the date of the last evaluable (non missing and non "Not Evaluable") tumor assessment.
- If an event (progression or death without previously documented PD) is observed after more than 2 missed study visits (using visit days as planned in the protocol for calculation) from last tumor assessment, the patient will be right-censored at the date of the last evaluable tumor assessment.
- Subjects who start new anti-cancer treatment prior to an event will be censored on the date of the last evaluable tumor assessment before anti-cancer therapy is given.
- Subjects who do not have a baseline tumor assessment or who do not have any post-baseline
 tumor assessments will be censored on the date of first dose unless death occurred on or before
 the time of the second planned tumor assessment in which case the death will be considered an
 event.

PFS = (date of PD or death/censoring - date of the first dose + 1)/30.4375 (months).

The date of PFS event / censoring will be defined in Table 7.

Table 7 Progression-free Survival Event / Censoring

PFS Event Status		Censoring	Date of event / censoring	
Progressed or died	Before any planned tumor assessment or within two subsequent scheduled tumor assessments after last response assessment of CR, PR or SD	Event	Minimum(Date of PD, Date of death)	
	Otherwise	Censored	Date of last tumor assessment with outcome CR, PR or SD or date of first dose, whatever is later	

PFS Event Status	Censoring	Date of event / censoring
Neither progressed nor died	Censored	Date of last tumor assessment with outcome CR, PR or SD or date of first dose, whatever is later

PFS: progression-free survival, CR = Complete Response, PR = Partial Response, SD = Stable Disease, PD = Progressive Disease.

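### SAP 14.1 makes best overall response depend on an on-treatment scan that the schedule never provides, and it counts scans taken after new anticancer drugs or radiotherapy

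*SAP*

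**What the plan says.** **Evaluability.** SAP 14.1 (Best Overall Response): "If a subject has missing baseline tumor assessment and/or no tumor assessment on-treatment, BOR will be NE". SAP section 9 defines one on-treatment period, headed as being for safety analyses. It runs from treatment day 1 "until the last M3541 administration date + 30 days (PTD 30"), or to an earlier date if subsequent anticancer therapy or the data cut-off comes first. Section 14.1 does not cite it. For its spider and waterfall plots, 14.1 uses a different term: "Subjects with no baseline tumor assessment or without any post-baseline tumor assessment will not be included".

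**Scan timing.** Protocol Table 1, footnote n: tumor assessments "are to be completed every 6 weeks beginning on PTD 42 of the Mid-term Safety Follow-up period". The visit window is ± 7 days. SAP 14.1 also starts its count of assessments at PTD 42.

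**Which scans count.** SAP 14.1 takes the best response until progression, "excluding assessments after tumor surgery". It has no rule for scans after new drugs or radiotherapy. For PFS, SAP 14.2 does: "Subjects who start new anti-cancer treatment prior to an event will be censored on the date of the last evaluable tumor assessment" before that therapy is given. Section 9 adds: "As a general rule, unscheduled assessments will always be included in the analysis".

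**Later therapy.** Protocol 6.5.2 restricts other anticancer therapy during treatment and the DLT follow-up period, which now covers PTD 1 to 14. The same section allows radiotherapy to other lesions (involving less than 30% of bone marrow) beyond PTD 7. Table 1, footnote n, says scans are not required once a new antitumor treatment has started.

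**The concern.** The two problems follow one from the other.

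1. The evaluability condition uses a term that no scheduled scan can satisfy, whether *on-treatment* means the dosing days or the period in section 9. A literal program would return Not Evaluable for subjects the section means to evaluate, and those subjects would stay in the ORR denominator.
2. Once the condition is read as intended, scans from PTD 42 onward count whatever drug or radiotherapy came first. The two secondary activity endpoints then treat the same scan differently: PFS stops before new therapy and BOR does not. The trial has no control arm, so shrinkage caused by off-protocol treatment would be tabulated as response to M3541 plus RT.

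ORR is reported by dose level with exact 95% intervals, confirmed and unconfirmed. With planned cohorts of 3, one misattributed response is visible in the table.

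**Working it through.** The documents give no figure for BOR or ORR to reproduce. The check is day arithmetic, followed by exact intervals on assumed counts.

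**Inputs**
- Treatment starts on a Monday, with 10 fraction days and one weekend break (Protocol 5.1): FD 1 = day 1, FD 10 = day 12.
- PTD 1 is the day after the last dose (Protocol Table 1, footnote b), so PTD p = day 12 + p.
- On-treatment end: last M3541 dose + 30 days (SAP section 9).
- First scan: PTD 42 ± 7 days (Protocol 7.1.4 and Table 1).
- SD minimum: 6 weeks − 7 days from the first day of treatment (SAP 14.1).

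**Part 1: can a scheduled scan be on-treatment?**
- Latest on-treatment end: 12 + 30 = day 42.
- Nominal first scan: 12 + 42 = day 54; earliest: 12 + 35 = day 47.
- Gap: 47 − 42 = 5 days.
- With a 3-day treatment delay: end 15 + 30 = day 45, earliest scan 15 + 35 = day 50; the gap is again 5 days.
- If M3541 stops on day 1 but RT runs to day 12: end 1 + 30 = day 31, earliest scan day 47; gap 16 days.
- Subjects enrolled before protocol v5.0, taking PTD 1 as the third day after the last dose: earliest scan = last dose + 35 + 2 = last dose + 37; gap 37 − 30 = 7 days.

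No scheduled scan falls inside the window in any of these cases. Only an unscheduled or early-termination scan could. If all scans at a dose level are on schedule, the literal rule gives an ORR of 0% by construction. By contrast, the SD minimum is 42 − 7 = 35 days. A scan on day 47 already passes it, so the section plainly means that scan to count.

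**Part 2: how much room is there for later therapy before the first scan?**
- New drugs possible from PTD 15 = day 27.
- To the earliest scan: 35 − 15 = 20 days. To the nominal scan: 42 − 15 = 27 days.
- Radiotherapy to another lesion can start earlier still, beyond PTD 7.
- For subjects enrolled before v5.0 the DLT period ended at last dose + 23 days (SAP section 9), so the lead is shorter.

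**Effect on ORR (assumed: one response first seen after new therapy).** Clopper-Pearson limits are the 2.5% quantile of Beta(x, n − x + 1) and the 97.5% quantile of Beta(x + 1, n − x). For x = 0 the upper limit reduces to 1 − 0.025^(1/n).

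| n | Response not counted | Response counted |
|---|---|---|
| 3 | 0/3 = 0% (0–70.8%) | 1/3 = 33.3% (0.8–90.6%) |
| 6 | 0/6 = 0% (0–45.9%) | 1/6 = 16.7% (0.4–64.1%) |

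Three is the planned cohort size. Six is two cohorts at one dose level, which SAP section 9 pools. Unconfirmed ORR needs one such scan; confirmed ORR needs two, at least 4 weeks apart.

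**The case against.** **On part 1.** The section 9 definition is labelled for safety analyses. The safety sections cite it and 14.1 does not. Section 14.1 itself starts at PTD 42, and Protocol 7.3 says the response endpoints include assessments made after the end of study treatment. On this view the slip is one of terminology and a sensible programmer would read it correctly. That is fair as to intent, and the all-Not-Evaluable result belongs only to the literal reading. But the sentence is a derivation rule, and it is false on either meaning of the term.

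**On part 2.** Protocol 7.1.4 and Table 1, footnote a, treat tumor assessments as no longer applicable once a new treatment starts, which is stronger than the waiver in footnote n. The planned listings and the swimmer plot (14.2) would show a response that followed new therapy. The PFS comparison is also imperfect, because the protocol counts onset of other anticancer therapy as a PFS event while the SAP censors, and two endpoints need not share one rule. These points limit the problem and make it detectable, but they do not remove such scans from the BOR and ORR tables. Routes for the scans remain:
- An early end of study calls for all PTD 365 assessments (Table 1, footnote a).
- Planned scans continue when study therapy is not completed (Protocol 5.5.1), and starting other anticancer therapy is a listed reason for stopping M3541.
- Unscheduled assessments are always included.
- Nothing says whether permitted radiotherapy to another lesion counts as a new treatment, and that lesion may be a target lesion.

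**On magnitude.** The one-response example is hypothetical and its intervals overlap heavily. That stands, and it limits how much weight the example can carry.

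**Conclusion.** The concern holds on both counts. As written, the evaluability rule excludes every scheduled scan, by at least 5 days. As intended, BOR has no cut-off for later drugs or radiotherapy, although new drugs are possible 20 to 27 days before the first scan under the current protocol. The day counts assume a Monday start and PTD 1 on the day after the last dose. The frequency of scans after new therapy is unknown, so the ORR shifts above show what one case would do and are not an expected bias. BOR is a descriptive secondary endpoint, and the DLT analysis and dose decisions do not depend on it. It should be fixed before BOR is programmed.

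**What to change.** Make two edits in SAP 14.1:

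1. In the evaluability sentence, replace the on-treatment condition with *no evaluable post-baseline tumor assessment*.
2. Replace the surgery-only exclusion with one for assessments made after the start of any subsequent anticancer drug therapy, radiotherapy or tumor surgery.

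Apply the second rule to BOR, confirmed BOR, ORR and the best-change waterfall plots in 14.1 and 14.3, which at present state no therapy exclusion.

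No new data are needed. Section 9 already derives the date ("Subsequent anticancer drug therapy date will be based on" the post-discontinuation drug, radiotherapy and surgery pages), and 14.2 uses the same pages. The cost is that some subjects may become Not Evaluable because their only scans follow later therapy, including local radiotherapy to a single lesion. The rule should therefore be fixed before the data are reviewed.
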